6.1.7. Safety Measures: Neurologic Examination (Neuropathy Impairment Score [NIS])

The change from Baseline in the NIS for Weeks 2, 4, 8, 16, 24, 32, 40, 48, 56, 64 and 80 will be summarized. The number and percentage of subjects whose NIS score worsened (change>0), improved (change<0) or had no change will also be shown. Missing data will be imputed using LOCF only. For this analysis, Baseline data will not be carried forward in the case of a post-Baseline observation not being available for use in LOCF. An additional analysis will use the change from Baseline to the largest (worst) post-Baseline value and to the last post baseline value. The last post baseline value will only be used in the summary of change from baseline (not be used in the summary with change categories).

Neurological-related safety data

The “conclusion from the neurological examination” data will be summarized for each timepoint and the final assessment over all neurological examinations for each subject. In addition the persistence of any neurological examination finding will be summarized, showing the incidence of subjects with new or worsened neurological examination abnormality (both clinically significant only and also for any finding) for 2, 3, 4, and ≥ 5 consecutive visits.

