9.1. Sample Size Determination

In terms of the study feasibility and the safety evaluation described below, the total sample size will be approximately 200 subjects (170-220 subjects, approximately 66 subjects [56-73 subjects] per treatment group). However, it is acceptable to randomize more than 220 subjects from the safety perspective as described below because primary objective is to evaluate the long-term safety.

Japanese subjects are enrolled in two studies within the tanezumab CLBP program (A4091059 and this study). In ongoing A4091059 study (randomization was finished in June 2017), 129 Japanese subjects were randomized and appropriately 57 Japanese CLBP subjects are expected to be initially randomized to the tanezumab arm. Considering approximately 133 (113-146) subjects are expected to be randomized to the tanezumab arm in this study, the safety data will be collected from approximately 190 (170-203) Japanese CLBP subjects treated with tanezumab.

The primary objective of this study is the evaluation of long term safety. The number of subjects who complete this study is estimated as described below. Both these protocols

require subjects to meet the efficacy response criteria (defined as at least a 30% reduction in weekly average LBPI score at week 16 relative to Baseline and at least a 15% reduction in weekly average LBPI score from Baseline at any week from week 1 to week 15) at week 16 in order to continue in the study. The proportion of 30% responders at week 16 was approximately 60% in two OA phase 3 studies (A4091011, A4091014) and approximately 42% in one CLBP phase 3 study (A4091012). On the other hand, the proportion of subjects discontinuing after week 16 is assumed to be approximately 10% for OA and approximately 20% for CLBP based on the results of discontinuation for reasons other than insufficient clinical response in these studies.

Therefore, the proportion of subjects expected to complete this study was calculated as approximately 54% ($=100*0.6*0.9$) based on the two OA studies and approximately 34% ($=100*0.42*0.8$) based on the CLBP study, and the proportion of completers of this study is estimated to be between 34% and 54%. Table 6 shows the relationship between the proportion of completers and the number of subjects with one year exposure.

From Table 6, if the proportion of completers is at least 43% in the CLBP program, approaching 100 subjects are expected to be treated with tanezumab for a minimum of one year.

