- The NIS is the sum of scores over all 37 items from both the Left and Right side. The change from baseline to each post-baseline visit in the NIS will be summarized. The change from Baseline to each study visit, and to Worst (largest) change from Baseline (over all post-Baseline visits) will be summarized.
- The neurological consultation data will be summarized all subjects, and for subjects with adverse events of abnormal peripheral sensation, which are described in the Neurological Examination Section (Section 7.3.9). The “conclusion from the neurological examination” data will be summarized for each timepoint, and as well as a summary of the final assessment over all neurological examinations for each subject.
- The incidence of subjects with any of the joint safety adjudication outcomes of rapidly progressive osteoarthritis (type-1 and type-2), subchondral insufficiency fracture (or SPONK), primary osteonecrosis, or pathological fracture will be shown by number of subjects treated and subject years of exposure (treatment plus follow-up periods), for individual treatment groups and differences between tanezumab treatment groups and the celecoxib treatment group. The risk ratio and risk difference with 95% Confidence intervals will be calculated for the comparisons of each tanezumab group versus the celecoxib group. The time to each event will be summarized, and (where there are sufficient numbers of subjects) Kaplan-Meier estimates of the time to event will be produced.
- The incidence of subjects with any of the joint safety adjudication outcomes of rapidly progressive osteoarthritis (type-2), subchondral insufficiency fracture (or SPONK), primary osteonecrosis, or pathological fracture will be analyzed as described above. In addition the same analysis will be performed for the individual events of all-cause Total Joint Replacements, and adjudicated outcomes of rapidly progressive osteoarthritis (type 1, type 2 and both types 1 and 2 combined), subchondral insufficiency fracture (or SPONK), primary osteonecrosis and pathological fracture.

- A listing of the subjects who develop anti-tanezumab antibodies after treatment for each dose, and the proportion of subjects who develop anti-tanezumab will be summarized for each dose.
- The PK profile will be examined for subjects with anti-tanezumab antibodies.
- Individual subjects with positive ADA results will be evaluated for potential ADA impact on the individual's efficacy and safety profile.

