3. ENDPOINTS AND BASELINE VARIABLES: DEFINITIONS AND CONVENTIONS

3.1. Primary Endpoints

Safety Measures

- *Adverse events.*
- *Standard safety assessments (safety laboratory testing [chemistry, and hematology], vital signs).*
- *Orthostatic (supine/standing) blood pressure assessments.*
- *Survey of Autonomic Symptoms (SAS) scores.*
- *Electrocardiogram (ECG, 12-lead) assessments.*
- *Joint Safety adjudication outcomes.*
- *Total joint replacements.*
- *Neurologic examination (Neuropathy Impairment Score [NIS]).*
- *Anti-drug antibody assessments (ADA).*
- *Physical examinations.*
- *Outcome of Consultation*

The details of the safety endpoints are described in [Section 3.5](#).

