The Baseline mean will be calculated using potential five values of the Initial Pain Assessment Period (IPAP). Note, for the weekly pain score, a pain score being carried forward with LOCF might not be a visit week assessment (eg, carry forward Week 3 for missing Week 4 data). For the purposes of the imputation analyses, where there is no post-baseline observation available to carry forward, then the baseline score carried forward will be the baseline average pain score, being the mean of the expected five pain scores in the baseline assessment period. If any of the baseline average pain scores are missing (or there are less than 5 pain scores) then the baseline is calculated over the remaining non-missing values.

For the analysis of NIS, the Baseline observation will not be carried forward in the case where a post-baseline observation is not available for the LOCF imputation.

For the other efficacy and safety analyses, the observed data (no imputation for missing data) will be summarized if not otherwise specified. Additional analyses will be performed in order to explore the sensitivity of the efficacy analysis results to missing data as described in this section.

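### By-visit NIS uses LOCF as its only missing-data method to Week 80, so about 40–66% of Week 56 values would be carried forward and the late columns do not show NIS under long-term exposure

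*SAP*

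**What the plan says.** - SAP 3.1 lists NIS among the primary (safety) endpoints.
- SAP 6.1.7 states: "The change from Baseline in the NIS for Weeks 2, 4, 8, 16, 24, 32, 40, 48, 56, 64 and 80 will be summarized". Counts of subjects who worsened, improved or did not change accompany the means. The same paragraph says: "Missing data will be imputed using LOCF only".
- SAP 5.3 adds one limit: "For the analysis of NIS, the Baseline observation will not be carried forward" when a subject has no post-baseline exam. Elsewhere in 5.3, observed data are the default unless another method is specified. NIS is therefore a deliberate exception, and no observed-data by-visit NIS table is named.
- Protocol 9.2 says: "The change from baseline to each post-baseline visit in the NIS will be summarized". It also asks for the worst change, and it is silent on imputation.
- Protocol 7.3.9 and Table 2 require NIS at the early-termination visits, which fall 8, 16 and 24 weeks after the last SC dose.
- The on-/off-treatment rule in SAP 6.2 is confined to efficacy. The general visit-window table in SAP Appendix 2.1 is written for efficacy observations and ends at Week 64, whereas NIS is reported at Week 80. Nothing says which NIS exams LOCF may carry.
- Protocol 9.1 expects heavy attrition: "the proportion of completers of this study is estimated to be between 34% and 54"%.

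**The concern.** The primary objective is long-term safety, and the Week 40–56 columns of the NIS table are where a reader would look for a neurologic effect that builds with repeated dosing. Subjects who fail the Week 16 pain criterion have had two injections, the last at Week 8. LOCF keeps them in every later column beside completers who have had up to seven.

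Two things are at stake. The late-visit mean and the worsened/improved counts mix short and long exposure in unstated proportions. The displayed n also suggests that many more subjects were examined at that visit than actually were, which makes the summary look more precise than it is.

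**Working it through.** **1. Reproduce the protocol's completer figures (protocol 9.1).** Completers = Week 16 responder share × (1 − later discontinuation).
- Osteoarthritis basis: "The proportion of 30% responders at week 16 was approximately 60% in two OA phase 3 studies", with 10% stopping later. 0.60 × 0.90 = 54.0% (stated 54%).
- Low back pain basis: 42% responders, 20% stopping later. 0.42 × 0.80 = 33.6% (stated 34%).

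Both reproduce. Non-completers are 46.0% and 66.4%.

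**2. Split the non-completers.** The protocol's arithmetic has no separate term for stopping before Week 16, so everyone who does not pass is treated as leaving at the Week 16 criterion.
- Osteoarthritis basis: 40% at Week 16, then 0.60 × 0.10 = 6% later.
- Low back pain basis: 58% at Week 16, then 0.42 × 0.20 = 8.4% later.

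Week 16 failures are 0.40/0.46 = 87% and 0.58/0.664 = 87% of non-completers.

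**3. Find who has a real exam at Week 56.** Early-termination exams fall at last dose + 8, + 16 and + 24 weeks.

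| Last SC dose (week) | Exams after it (weeks) | Exam at Week 56? |
|---|---|---|
| 8 | 16, 24, 32 | no |
| 16 | 24, 32, 40 | no |
| 24 | 32, 40, 48 | no |
| 32 | 40, 48, 56 | yes |
| 40 | 48, 56, 64 | yes |
| 48 | 56, 64, 72 | yes |

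The carried share at Week 56 is therefore at least the Week 16 failures and at most all non-completers: 40–46% (osteoarthritis basis) or 58–66% (low back pain basis). If later stops are spread evenly over last doses at Weeks 16–48, two of the five dose points are carried: 0.40 + 0.06 × 2/5 = 42%, and 0.58 + 0.084 × 2/5 = 61%. At 66 per arm, the ranges are about 26–30 or 38–44 carried values.

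**4. Find which exam is carried for a subject last dosed at Week 8.**
- If early-termination exams feed LOCF, it is the Week 32 exam, 24 weeks (168 days) after dosing. At the 17–24 day half-life in protocol 1.2.4.6.1, that is 168/24 = 7 to 168/17 = 9.9 half-lives.
- If only treatment-period exams feed LOCF, it is the Week 16 exam, 8 weeks after dosing, which the SAP's efficacy rule would call on-treatment.

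**5. Effect on the mean.** Let *c* be the carried share and *f* the fraction of the Week 56 on-treatment effect present in carried values (*f* is an assumption). Reported mean ÷ on-treatment effect = (1 − *c*) + *c* × *f*. With all non-completers carried (*c* = 0.46 or 0.664):

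| *f* | *c* = 0.46 | *c* = 0.664 |
|---|---|---|
| 0 | 54% | 34% |
| 0.5 | 77% | 67% |
| 1 | 100% | 100% |
| 1.25 | 112% | 117% |

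At the lower carried shares (0.40 and 0.58), the *f* = 0 values are 60% and 42%.

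**6. Effect on n and SE.** The examined share runs from 60% down to 34%. Displayed n ÷ examined n = 1/0.60 = 1.7 to 1/0.34 = 2.9. At equal SD the SE looks √1.67 = 1.3 to √2.94 = 1.7 times too small. This illustration is separate from the *f* = 0 case, because a block of zero changes would also alter the SD.

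**The case against.** The strongest reply is that LOCF for NIS is deliberate, is stated consistently in two sections, and feeds a descriptive table with no hypothesis test. It is also not the only neurologic evidence. SAP 6.1.7 plans worst and last change, the examination conclusion at each timepoint, and persistence of new or worsened findings over consecutive visits. SAP 6.1.8 adds consultations, and SAP 6.1.1 tabulates adverse events of abnormal peripheral sensation. LOCF does not touch the worst-change, conclusion, persistence or consultation summaries, and the conclusion and persistence summaries carry time information. All of this stands and lowers the severity. None of it gives the NIS itself by visit in the subjects actually examined.

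A second reply also stands. Observed late columns mainly represent Week 16 pain responders who stayed on treatment, so an observed-data table used alone could hide harm in those who left. That is a reason to keep LOCF as a labelled companion table.

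A reader might infer more than the documents support:
- *That 46–66% of Week 56 values are carried.* That is the share not completing treatment. Subjects last dosed at Weeks 32–48 can have a real exam near Week 56, so the lower bound is 40%.
- *That carried values are mostly off-drug.* This follows only if early-termination exams feed LOCF, which the SAP leaves open.
- *That LOCF must pull a real effect toward zero.* The direction depends on *f*. LOCF also retains a worsened score in a subject who stopped, and protocol 7.4.1 and 7.4.3 provide for stopping treatment after certain sensory or autonomic events.
- *That protocol 9.2 rules out imputation.* It does not mention it, and protocol section 9 allows the SAP to modify its plans.
- *That the full ITT n would be shown.* Baseline is not carried forward, so subjects with no post-baseline NIS drop out.

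**Conclusion.** The concern holds in a limited form. On the protocol's own attrition figures, roughly two-fifths to two-thirds of the Week 56 NIS values would be copied from earlier exams, mostly in subjects who had two injections. On either reading of which exam is carried, the Week 40–56 columns do not describe NIS under long-term exposure.

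The 40–66% range assumes that the protocol's attrition applies, that follow-up exams are attended, and that they are assigned by study day. The dilution figures are conditional on *f*, which no document gives, and the SE figures on equal SD. The plan does not demonstrate that harm would be masked. It shows a by-visit safety table that cannot be interpreted as written, and an unstated rule for which exams feed it. Severity is moderate, because the analysis is descriptive and other neurologic summaries are unaffected.

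**What to change.** In SAP 6.1.7 and 5.3:

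1. Add an observed-data by-visit NIS summary with n examined at each visit, for both mean change and the worsened/improved/no-change counts.
2. State which exams feed LOCF (treatment-period only, or early-termination visits as well) and how NIS exams are assigned to visits through Week 80.
3. Label the LOCF table as supportive.
4. Keep the worst-change and last-value summaries for all treated subjects.
5. Show follow-up exams by weeks since the last SC dose.

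The data are already collected, so the cost is SAP wording and the programming of one table family. The downside is that n falls at late visits and those columns over-represent Week 16 responders, so a footnote should direct the reader to the worst-change summary alongside them.

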6.1.8. Safety Measures: Outcome of Consultation

Summary of neurological consultation will be shown. The number of subjects with at least 1 adverse event requiring neurological consult, and whether or not a neurologic consult performed, and the expert primary diagnosis will be summarized. Further details of neurological consultation will be summarized.

Summary of incidence of sympathetic neuropathy based on investigator assessment and, if performed, expert consultant assessment will be shown.

6.1.9. Safety Measures: Anti-drug Antibody Assessments (ADA)

The following assessments of ADA data will be made using all available data:

- A listing of individual serum ADA results sorted by treatment group, subject ID and planned visit. The listing will also include the actual test date/times.
- The proportion of subjects who test positive (ie, develop anti-tanezumab antibodies) and negative will be summarized by treatment group and planned visit. The summary will also include the proportion of subjects who test positive and negative overall in the study.
- Subjects who develop anti-tanezumab antibodies after treatment will be evaluated for the presence of anti-tanezumab neutralizing antibodies, and individual results will be listed.

Individual subjects with positive ADA results will be evaluated for potential ADA impact on the individual’s efficacy and safety profile.

6.1.10. Safety Measures: Physical Examinations

The following non-standard safety tables will also be included:

- Incidence of physical examination findings at screening.
- Incidence of musculoskeletal physical examination findings at screening.

6.2. Secondary Endpoints

All analyses in this section use the ITT analysis set, if not otherwise specified. If not otherwise specified, the observed data (no imputation for missing data) will be summarized.

All efficacy assessments during the treatment period are made on the analysis windows defined in [Appendix 2.1](#). Using these windows we find the analysis window for a patient's last subcutaneous (SC) dose. Any data included in a window that is up to 8 weeks from this last SC dose window is 'on-treatment', and any data included in a window that is more than 8 weeks after the last SC dose window is off-treatment. Data in on-treatment analysis windows will be used in summaries and analyses, while data in off-treatment analysis windows will be excluded from all summaries and analyses of treatment period efficacy data, ie, up to Week 56.

Efficacy data collected via subject diary (aLBPI and rescue medication use) are collected daily or weekly, not at study visits. Diary efficacy data will be considered on-treatment if it is collected up to 84 calendar days after the last SC dose. Diary efficacy data collected more than 84 calendar days after the last SC dose will be considered off-treatment and excluded from summaries and analyses of treatment period efficacy data.

